5.3.2 Clinical Laboratory Tests

Clinical laboratory safety tests will be performed in a licensed, central clinical laboratory. Urine pregnancy and urinalysis tests may be performed at the site using a licensed test (dipstick). Any laboratory test result that fall outside of the normal ranges may be repeated at the discretion of the Investigator, A urine sample may be sent to the central laboratory for evaluation of urine chemistry if clinically indicated (as judged by the investigator/designee). New medically significant abnormal laboratory results, which in the opinion of the investigator are related to safety, should be repeated as soon as possible (preferably within 24 to 48 hours). Any medically significant change in laboratory evaluations will be recorded as an AE (for the definition of AE see Section 6.1.1).

The following clinical laboratory tests will be performed (see Table 5.2-1 for the schedule of tests):

MedImmune CAM-3001 Serum Chemistry

- Calcium
- Potassium
- Sodium
- Aspartate transaminase (AST)
- Alanine transaminase (ALT)
- Alkaline phosphatase (ALP)
- Gamma glutamyl transferase (GGT)
- Total bilirubin
- CRP
- Erythrocyte sedimentation rate (ESR) locally tested

Note for serum chemistries: Tests for AST, ALT, ALP, and total bilirubin must be conducted and assessed concurrently.

Haematology

- Haemoglobin
- Leukocyte count
- Leukocyte count differential
- Reticulocytes

Urinalysis

- Blood
- Protein/Albumin
- Protein

If clinically indicated, urine chemistry:

• Creatinine, microalbumin and microalbumin/creatinine ratio

Pregnancy Test (females of childbearing potential only)

- Serum beta- human chorionic gonadotropin (hCG) (at Screening only)
- Urine hCG

Other Safety Tests

Additional laboratory tests will be performed at Screening and are listed below. A laboratory manual will be provided specifying specific procedures for collection, processing, storage, and shipping of samples.

- Hepatitis A antibody, hepatitis B surface antigen, hepatitis C antibody
- Virology; CMV and EBV

- Urea
- Creatinine
- Albumin
- Total cholesterol
- Triglycerides
- Rheumatoid factor
- Anti-CCP antibodies
- Glucose

- Platelet count
- Mean corpuscular volume (MCV)
- Mean corpuscular haemoglobin concentration (MCHC)
- Glucose
- Nitrite

Protocol MI-CP219; Amendment 3

Final

MedImmune Protocol MI-CP219; Amendment 3 CAM-3001 Final 5.3.3 Pharmacokinetic and Immunogenicity Evaluation and Methods

For PK analyses, it is important that the exact time of the SC injection and of each PK sample taken is recorded for each subject. Serum samples will be collected predose at designated visit days starting with Study Day 1 for CAM-3001 level and anti-CAM-3001 antibody determination. Specific procedures for sample collection, processing, storage, and shipment can be found in a separate laboratory manual provided to sites. CAM-3001 serum concentrations and anti-CAM-3001 antibody detection will be measured using Enzyme-linked immunosorbent assay and ECL assays, respectively.

5.3.4 Disease Evaluation and Methods

A clinical evaluation of disease activity should be done as described in the Study Reference Manual. This evaluation will encompass DAS28 and ACR responses.

5.3.4.1 DAS28

The DAS28(CRP) has been validated against radiographic progression and physical function (HAQ-DI) and the validation profile is similar to the DAS28 Erythrocyte Sedimentation Rate (ESR) (Wells et al, 2009). In this study both CRP and ESR will be collected. Subjects are required to have at least moderately active disease as defined by DAS28 \geq 3.2 at Screening and Day 1 in order to be included in this study. The investigator will calculate DAS28(CRP) for Screening and DAS28(ESR) for Day 1 to assess this criterion.

The DAS28 considers 28 of the 68 tender joint count (TJC) and 28 of the 66 swollen joint count (SJC), general health (GH) using patient assessment of disease activity using the numerical rating scale with 0 = best, 100 = worst, plus levels of CRP (mg/L) or ESR (mm/hour).

DAS28(CRP) values will be calculated as follows (Wells et al, 2009):

DAS28(CRP) = 0.56 * sqrt(TJC28) + 0.28 * sqrt(SJC28) + 0.014*GH + 0.36 ln(CRP+1) + 0.96

DAS28(ESR) values will be calculated as follows:

DAS28(ESR) = 0.56 * sqrt(TJC28) + 0.28 * sqrt(SJC28) + 0.70*ln(ESR) + 0.014*GH

DAS28 will be categorised using the EULAR response criteria:

Protocol MI-CP219; Amendment 3 Final

Baseline DAS Score	Level of Improvement from Baseline (Day 1)									
	> 1.2	\geq 0.6 to \leq 1.2	< 0.6							
< 3.2	Good response	Moderate response	No response							
\geq 3.2 to \leq 5.1	Moderate response	Moderate response	No response							
> 5.1	Moderate response	No response	No response							

Table 5.3.4.1-1DAS28 Improvement

DAS = Disease Activity Score

DAS28 defined remission is DAS28 of < 2.6. Low disease activity is < 3.2 and high disease activity is > 5.1.

5.3.4.2 ACR20, ACR50, and ACR70 Responses

The core components of the ACR response criteria are:

- Swollen joint count (66 joints; see below for details)
- Tender joint count (68 joints)
- Physician global assessment of disease activity (0-10 visual analogue scale [VAS]; see below for details)
- Patient global assessment of disease activity (0-100 VAS; see below for details)
- Patient pain assessment (0-100 VAS; see below for details)
- Patient reported functional disability (HAQ-DI; see below for details)
- Acute phase reactant (CRP and ESR)

A subject has an ACR response if all of the following occur:

- An improvement in the swollen joint count (66 joints)
- An improvement in the tender joint count (68 joints)
- An improvement in at least 3 of the following 5 assessments:
 - Physician global assessment of disease activity
 - Patient global assessment of disease activity
 - Patient pain assessment
 - Patient reported functional disability using the HAQ-DI
 - CRP or ESR

MedImmune CAM-3001 Subjects will be considered to have had an ACR20, ACR50 or ACR70 response if at least a 20%, 50% or 70% improvement from Day 1 (respectively) was observed in the criteria specified above.

68 Joint Assessments

The 68 joints to be assessed for tenderness are: temporomandibular (n = 2), sternoclavicular (n = 2), acromioclavicular (n = 2), the 8 proximal interphalangeal joints of the fingers, the interphalangeal joints of the thumbs (n = 2), the 8 distal interphalangeal joints, the 10 metatarsophalangeal, the 10 metacarpophalangeal joints plus the wrists (n = 2), elbows (n = 2), shoulders (n = 2), hips (n = 2), ankle mortise and tarsus (n = 4), knees (n = 2), and toes (n = 10) (Felson et al, 1993).

The 66 joints assessed for swelling are the same as those assessed for tenderness, except the hip joints are not included.

In order to calculate the ACR and DAS28 responses, each of the 68 joints will be evaluated for tenderness and swelling. Standardised metrology training will be provided if necessary.

Physician Global Assessment of Disease Activity

The physician global scale is a 10 cm VAS that asks the safety assessor to rate their subject's level of disease activity due to RA **'TODAY'.** Higher scores on this scale indicate increased (worse) disease activity.

Patient Global Assessment of Disease Activity

Subjects in the study will be asked to complete the patient global assessment of disease activity. The patient global assessment of disease activity is a measure of patient's general health as a result of their arthritis on a VAS of 0 (= very well) to 100 (= very poorly). Higher scores on this scale indicate worse health.

Patient's Pain Assessment

Subjects in the study will be asked to complete pain assessment. The Pain VAS scale measures patient's severity of pain 'TODAY' as a result of their arthritis on a VAS of 0 (= no pain) to 100 (= severe pain). Higher scores on this scale indicate worse pain.

The HAQ-DI will be used to assess the functional status of each subject (Fries et al, 1980). This 20-question instrument assesses the degree of difficulty a person has in accomplishing tasks of daily living in 8 functional areas (domains; dressing, arising, eating, hygiene, walking, reaching, grip, and errands/chores) over the past week. Scores range from 0 (without any difficulty) to 3 (unable to do). The highest scoring item in each domain is chosen. If an aid or device is used, or if assistance is required from another individual, then minimum score for that section is 2. The final scores are equal to the mean of these 8 highest scores and range from 0 to 3, with higher scores indicating greater functional disability. Additionally, subjects are asked to assess the severity of pain in the past week on a 100 mm VAS with 0 being no pain and 100 being severe pain. (Fries et al, 1980).

Final

The global disease activity and pain assessments, modified Borg scale, HAQ-DI, FACIT-Fatigue, SF-36 and MOS-Sleep Scale questionnaires are all self-administered and are to be completed by the subject without the assistance of the investigational site personnel.

All questionnaires should be completed before any other study procedures are conducted at the visit.

5.3.4.3 Other Patient Reported Outcomes

Functional Assessment of Chronic Illness Therapy-Fatigue (FACIT-Fatigue)

The FACIT-Fatigue is a 13 item subject-completed questionnaire to assess the impact of fatigue over the past 7 days. Responses range from 0 "Not at all" to 4 "Very Much". Final scores are the sum of the responses (0-52) where higher scores indicate greater fatigue (Yellin et al, 1997). Changes in scores > 3-4 points are considered to be clinically meaningful (Cella et al, 2002).

SF-36

The SF-36 is a validated instrument for measuring a person's general health status (Ware et al, 1993) over the past 4 weeks. The SF-36 includes 8 domains: Physical Function, Role Limitations-Physical, Vitality, General Health Perceptions, Bodily Pain, Social Function, Role Limitations-Emotional, and Mental Health and can be summarised into 2 summary scores, the Physical Component Summary and the Mental Component Summary. Final scores for the each scale range from 0-100 with higher scores indicating better health. The general

MedImmuneProtocol MI-CP219; Amendment 3CAM-3001Finalpopulation has a mean score of 50 with a standard deviation of 10. Changes of \geq 3-5 points inany of the summary scales or the individual scales are considered meaningful clinicallyimportant differences (Ware et al, 2007).

MOS-Sleep Scale

Medical Outcomes Study sleep questionnaire is a 12-item measure of sleep quality and quantity. Items are scored on a 5- to 6–point scale and responses to the questions are used to calculate aggregate scores for sleep adequacy, sleep disturbance, snoring, waking with shortness of breath or with a headache, somnolence, sleep index I (6-items), and sleep index II (9-items). All scales are scored on a 0-100 scale. For sleep adequacy, higher scores meant better sleep adequacy. For all other scales, lower scores indicated better sleep outcomes (Spritzer et al, 2003)

5.3.5 Correlative Studies

5.3.5.1 Exploratory Research

Samples will be obtained and analysed for exploratory research, that may include measurement of serum biomarkers, GM-CSF levels, analyses of serum autoantibodies and miRNA and/or mRNA expression. Analysis of the serum proteome will be carried out through the use of a large multiplex quantitative platform for known analytes. The mRNAs and/or miRNAs will be selected by both their presence in the GM-CSF pathway as well as potential downstream effectors. These analytes will be identified using ex vivo stimulation experiments where healthy donor cells are treated with GM-CSF to identify transcripts and/or miRNAs that are induced. CAM-3001 will then be utilised to determine which of these induced analytes are subsequently neutralised.

For both mRNA and miRNA experiments, a minimum 2.5 mL of blood per subject per time point are required. Specimens are stored in PaxGene tubes prior to processing. Aliquots of serum may be frozen and stored for additional exploratory studies based on research findings.

5.3.5.2 Receptor Occupancy

Assays of GM-CSF receptor occupancy will be performed at a central laboratory using flow cytometric techniques. The study schedule outlines when these samples will be collected. Instructions for sample collection, processing, storage, and shipment can be found in a

MedImmune Protocol MI-CP219; Amendment 3 CAM-3001 Final separate laboratory manual provided to the sites. Receptor occupancy will be evaluated in only those countries that can collect viable samples.

5.3.5.3 DNA Sample (optional) and RNA Sample

To investigate characteristics associated with subjects' clinical response and safety, one blood sample (8.5 mL) may be collected at Screening and frozen at -20° C (or lower temperature) for DNA sample preparation. The sample will be frozen and stored until used in exploratory analyses. The collection of blood for DNA analysis is optional. The completion of a separate informed consent form (Informed Consent Form for DNA Analysis) is requested. Subjects who do not wish to have the DNA test done will still be eligible for the study. Subjects who elect to have the DNA test done may, at any time before the end of the study, request that the blood collected for DNA analysis be destroyed.

All specimen and subject identifiers must be removed from the DNA blood samples such that under no circumstances can the DNA blood samples be linked back to a specific subject.

For DNA, miRNA and mRNA analyses, all collected specimens are identified on the sample itself only by study number and sample-ID (which is accession number and aliquot designation). Collection kits are supplied for each subjects visit and sample type. Accession numbers are pre-assigned to those kits. When a subject's samples are collected at a time point (for DNA samples, this is Day 1; for miRNA and mRNA samples, this is Day 1 and postdose), all samples of a single type have a sample ID, which is an aliquot plus accession number. The aliquot designation varies within a single collection; however the accession number remains constant within that collection. There are no personal identifiers associated with the sample tube. Samples are stored in this manner.

All labelling and shipments of bio hazardous materials must comply with International Air Transportation Association regulations.

6 Assessment of Safety

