2.3 Exploratory Objectives

The exploratory objectives of this study may include the following:

- 1) To investigate the effects of CAM-3001 on:
 - Expression of proteins such as GM-CSF, biomarkers of disease activity, autoantibodies and other inflammatory proteins in serum
 - The potential relationships between inhibition of GM-CSF-inducible gene signature, clinical activity, GM-CSF receptor occupancy and drug concentration (PK) and the miRNA and/or mRNA expression pattern in the periphery of subjects enrolled.
 - Patient reported outcomes
- 2) To assess whether deoxyribonucleic acid (DNA) polymorphisms are associated with the safety or clinical response to CAM-3001 (optional for subjects)

3 Study Design

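### Section 5.3.5.3 contradicts itself on whether DNA samples can be linked to subjects: its unlinkability sentence conflicts with its own coding scheme, its destruction right and the genotype-response objective

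*Protocol*

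**What the plan says.** Protocol Section 5.3.5.3 sets an absolute rule: "All specimen and subject identifiers must be removed from the DNA blood samples", to the point that "under no circumstances can the DNA blood samples be linked back to a specific subject". It names no time for the removal, no holder of a key and no exception.

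The same section also says the following:

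- The sample has a subject-level purpose: "To investigate characteristics associated with subjects' clinical response and safety, one blood sample (8.5 mL) may be collected at Screening".
- Until the study ends, a subject who gave the sample may "request that the blood collected for DNA analysis be destroyed".
- DNA and RNA tubes carry the study number and a sample-ID made of an accession number and an aliquot designation. The tubes come from kits supplied by subject visit and sample type, with accession numbers assigned in advance. Storage is described in those terms.

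Elsewhere in the protocol:

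- Exploratory objective 2 in Section 2.3, repeated in the Study Abstract, is: "To assess whether deoxyribonucleic acid (DNA) polymorphisms are associated with the safety or clinical response to CAM-3001".
- Sections 7.3.3 and 7.3.3.2 list possible analyses of polymorphisms against safety signals and against clinical or safety responses.
- Section 11 has laboratory specimens sent outside the site identified by subject identification number, with no exception for DNA.

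On timing of collection, Section 5.3.5.3 states "one blood sample (8.5 mL) may be collected at Screening" and, further on, "for DNA samples, this is Day 1".

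**The concern.** An association between genotype and response can be estimated only if each genotype is joined to the same person's DAS28 result or adverse events. A destruction request can be carried out only if that person's tube can be found. Both need a route from tube to subject, and one sentence of the section forbids any such route.

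At stake are the exploratory DNA objective and two assurances to subjects, unlinkability and destruction on request, which cannot both hold over the same period. Cutting the link cannot be undone. A site or laboratory that acts on the strict sentence early loses the pairing for good, while one that follows the coding paragraph breaches the strict sentence.

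**Working it through.** No power, error rate or sample size enters, so there is nothing to recalculate. The check sets the statements side by side and asks of each whether it can stand with the unlinkability rule.

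1. **Specimen identifiers.** The rule removes every specimen and subject identifier. The coding paragraph of Section 5.3.5.3 keeps a sample-ID on the tube. A sample-ID is a specimen identifier, so the two conflict whatever the timing, unless the tubes are stripped later. No later stripping step is described.

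2. **Subject identifiers.** Section 11 puts a subject number on specimens leaving the site. This conflicts with the rule, and also with the coding paragraph, which allows only study number and sample-ID on the tube itself. The two can be reconciled if the subject number is reached through a key or accompanying record, but the protocol does not say so.

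3. **Destruction right.** It runs until the end of the study. Over that whole period the requester's tube must be findable. If the rule applies from collection, the right cannot be exercised. If it applies only after the study ends, both can stand. The protocol does not say which.

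4. **Association analysis.** Section 2.3 objective 2 and Sections 7.3.3 and 7.3.3.2 need genotype and outcome in one record per subject. If the link is cut before that record is built, the analysis cannot be done. If a de-identified genotype-outcome file is built first and the link cut afterwards, it can. The protocol does not state this order.

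5. **Collection time.** One phrase of Section 5.3.5.3 says Screening. A later paragraph of the same section, the DNA row of Table 5.2-1 and the Day 1 visit list in Section 5.2.2 say Day 1, and the Screening list has no DNA sample. One phrase is out of step with the rest.

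Steps 1 and 2 are contradictions as the text stands. Steps 3 and 4 become failures only if identifiers are removed before the study ends or before the data are joined. Step 5 is a slip with no bearing on linkability.

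**The case against.** The strongest reply is that coded samples were plainly intended. The coding paragraph is the operating procedure: it gives each tube an accession number from a kit tied to a subject visit and excludes only personal identifiers. A laboratory following it could probably trace a tube to a subject and join genotype to outcome. A right to destruction that ends with the study also fits anonymisation at study close. Details of timing, key custody and destruction could sit in the separate DNA consent form or the Laboratory Manual, neither of which is shown. The objective is optional for subjects, and the analyses are ones that may be done.

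Most of this stands as a limit on the consequence. A reader might infer that the DNA objective is impossible and wholly lost, and that no destruction request can be met. The documents do not support that, because it assumes that the strict sentence overrides the paragraph beside it and takes effect at collection.

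The reply does not remove the contradiction. The rule is mandatory and without exception, and likely intent is a reason to correct it. Nor is this a matter usually left to an analysis plan: how specimens are identified and what subjects are promised belong in the protocol and the consent form. Whether to anonymise or to code is a policy choice, and anonymisation with stated timing could also reconcile the text. Coding with a key is the smaller change, because the section already describes coded tubes.

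**Conclusion.** The contradiction is real and is in current text. The unlinkability sentence cannot stand with the retained sample-ID, the destruction right, the purpose of the sample or the specimen rule in Section 11. This is a stated rule at odds with a stated objective and a stated right, which is more than a missing detail.

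The consequence is conditional. If the sentence is applied literally at collection, genotype cannot be paired with outcome for any subject who gave a sample, and a destruction request cannot be carried out. If the coding paragraph is followed and the link is kept long enough, neither loss occurs. The protocol does not say how many subjects are expected to give the optional sample, so the size cannot be put as a number.

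The effect stops at one optional exploratory objective and the accuracy of what subjects are told. No primary or secondary analysis depends on it. The text should be corrected, and the Screening phrase is a minor correction to make at the same time.

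**What to change.** In Section 5.3.5.3, replace the unlinkability sentence with text to this effect: DNA tubes carry only the study number and sample-ID; a restricted key connects the sample-ID to the subject number; and the link is cut, if at all, only after the de-identified genotype-outcome file has been built and the period for destruction requests has closed.

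Reconcile Section 11 with this, for example by stating that DNA specimens are traced to the subject number through the key and do not carry that number on the tube. Check the DNA consent form, which is not shown, against the revised wording so that subjects are told the same thing.

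Change the collection time in the opening paragraph of Section 5.3.5.3 from Screening to Day 1, to match Table 5.2-1 and the Day 1 visit list.

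The cost is a wording change in the protocol, a change to the consent form if it proves inconsistent, and keeping a controlled key file until the link is cut.

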6.1 Safety Parameters

6.1.1 Adverse Events

The ICH Guideline for Good Clinical Practice E6(R1) defines an AE as:

Protocol MI-CP219; Amendment 3 Final

Any untoward medical occurrence in a patient or clinical investigation subject administered a pharmaceutical product and which does not necessarily have a causal relationship with this treatment. An AE can therefore be any unfavourable and unintended sign (including an abnormal laboratory finding), symptom, or disease temporally associated with the use of a medicinal product, whether or not considered related to the medicinal product.

An AE includes but is not limited to any clinically significant worsening of a subject's preexisting condition. An abnormal laboratory finding (including ECG finding) that requires an action or intervention by the investigator, or a finding judged by the investigator to represent a change beyond the range of normal physiologic fluctuation, should be reported as an AE.

Adverse events may be treatment emergent (ie, occurring after initial receipt of investigational product) or nontreatment emergent. A nontreatment-emergent AE is any new sign or symptom, disease, or other untoward medical event that begins after the subject signs the informed consent form but before the subject has received investigational product.

Elective treatment or surgery or preplanned treatment or surgery (that was scheduled prior to the subject being enrolled into the study) for a documented pre-existing condition that did not worsen from baseline (Day 1) is not considered an AE (serious or nonserious). Furthermore, flares of RA or signs and symptoms of RA should not be considered as AEs unless, in the opinion of the investigator, there is a significant worsening in intensity or frequency of the symptoms above the subject's baseline condition in which case it will be recorded as an AE in the eCRF.

